8.5. End of Study Visit

Participants who finish the 180-day visit will be considered "complete". They will then be provided with a \$35 gift card for completing the study and returning their devices (HeroTracker).

8.6. Participant Withdrawal

If premature withdrawal from the study occurs for any reason (including death) the investigator must determine the primary reason for withdrawal and record this information on the study

Withdrawal CRF. For participants who are lost to follow-up (i.e., those participants whose status is unclear because they fail to appear for study visits without stating an intention to withdraw), the investigator will show "due diligence" by documenting in the source documents the steps taken to contact the participant, e.g., dates of telephone calls, letters, emails, etc. If the participant fails to respond after 3 attempts they may be withdrawn from the study.

8.7 Accrual and Study Duration

We anticipate enrolling 4-5 subjects/week through the pulmonary clinic at the Hartford and Farmington locations. The Pulmonary Clinic at CCMC sees 15-30 patients/day at the Hartford location with 75% of the children having a diagnosis of asthma (~10-20/day), half of whom will be in the desired age range (~5-10) and will be screened. We will focus recruitment efforts on 2 days per week when the greatest number of patients are scheduled. To minimize selection bias, we will vary the time of day and day of the week in which we recruit. Therefore, enrollment should take approximately 16 weeks to complete and the study will conclude 6 months after that last subject is enrolled.

9. ADVERSE EVENT REPORTING

This is a non-significant risk study exploring the use of the BreatheSmart System in the management of children who present with poorly controlled asthma symptoms despite being managed on inhaled corticosteroids.

For the purposes of this study, the following anticipated adverse events and those meeting the definition of serious must be reported.

9.1. Recurrent Exacerbation of Asthma

An exacerbation of asthma requiring an intervention by the investigator must be recorded. The occurrence of these events will be obtained through both self-report and chart review. These events include:

- change in/or addition of prescribed medications for the treatment of asthma, or
- doctor visits outside of standard of care, or
- ER visits, or
- Hospitalization

9.2. Adverse Drug Reactions

Adverse reactions to medications prescribed for the treatment of asthma are well described in the literature. If an event related to a prescribed asthma drug meets the definition of serious it must be reported.

9.3. Serious Adverse Event Definition

A serious adverse event or reaction is any untoward medical occurrence that:

- Results in death
- Is life-threatening

- Requires inpatient hospitalization or prolongation of existing hospitalization
- Results in persistent or significant disability/incapacity, or
- Results in a congenital anomaly/birth defect

NOTE: The term "life-threatening" in the definition of "serious" refers to an event in which the patient was at risk of death at the time of the event; it does not refer to an event which hypothetically might have caused death if it were more severe. The investigator will be responsible for assigning causality to all serious adverse events.

In the event that a SAE leads to hospitalization, every effort should be made by the investigational site to obtain the medical records/discharge summaries and complete a Hospitalization CRF.

9.4. Death

In the event that the SAE leads to death, the Investigator should provide a narrative summary of circumstances, the events related to the death, and the primary cause of death, if known. Information regarding a participant's death must be reported within 24 hours of the knowledge of the death, and recorded on a Mortality form.

10. DATA MANAGEMENT

Prior to study enrollment, all research staff will be trained in principles of human subjects protection and maintenance of confidentiality of participant data.

10.1. Data Confidentiality

Participants limited PHI and the investigator's personal data, which may be included in the sponsor database, will be treated in compliance with all applicable laws and regulations. The sponsor will take all appropriate measures to safeguard and prevent access to these data by any unauthorized third party.

The investigator must take all appropriate measures to ensure that the protection of data for each study participant is maintained. The investigator, and all site staff involved in this study, may not disclose (or use for any purpose other than performance of the study), any data, record, or other unpublished confidential information disclosed to those individuals for the purpose of the study. Prior written agreement from Cohero Health must be obtained for the disclosure of any said confidential information to other parties. All information recorded on CRFs must be traceable to source documents in the participant's research file and/or medical chart with the exception of participant questionnaires that are completed directly in BreatheSmart or Qualitrics.

Study data will be directly captured into BreatheSmart. Participants and study personnel requiring access to research systems will be trained and must use their own login and password. Access to clinical study information in these systems will be based on individuals' roles and responsibilities and the minimum rule. These applications provide hierarchical user permissions for data entry, viewing, and reporting options. For optimum security, all communications between the users and the applications operate on a secured socket layer (SSL) using 128 and

256-bit encryption. The web servers are protected by a managed firewall from potential web and network attacks, and the networks are guarded by an intrusion detection and protection surveillance system against malicious threats. These applications are designed to be in full compliance with International Conference on Harmonization and Good Clinical Practices (ICH-GCP), the FDA's Code of Federal Regulations (CFR) Number 21 Part 11 Electronic Record and Electronic Signatures, the FDA's "Guidance: Computerized Systems Used in Clinical Trials, the Privacy Rule of the Health Insurance Portability and Accountability Act of 1996 (HIPAA), and Subtitle D of the Health Information Technology for Economic and Clinical Health (HITECH) Act, 2009

10.2. Data Monitoring

All questionnaires will be administered using the Qualtrics HIPAA-compliant web-based data collection software and app presented on encrypted and password protected iPads. All surveys administered at each visit (including the TAI, PedsQL, baseline data collection form, and follow up data collection form) are built into the Qualtrics platform. Qualtrics is a HIPPA-compliant electronic survey development and analytic tool. All data collected through Qualtrics will be stored into a pass-word protected Qualtrics account. PHI will not be entered into the database. Upon enrollment, subjects will be designated a study number. Once data is entered in the database, they will only be identified by study number. All communications with enrolled participants will be documented in a password protected ACCESS database on password-protected and encrypted computers in the Asthma Center. No PHI will be entered into this database.

Original source documents including the original signed consent form, HIPPA form, and any other relevant documents will be kept in a locked filing cabinet in a locked office until data analysis is complete. The PI will be responsible for monitoring the quality of the CRF completion and source documents.

10.3. Data quality

10% of the records will be spot checked on three separate occurrences: after completion of all data entry for baseline visits, 90 day follow-up visits and end of study visits (180 days post randomization). The rate of error and location of errors will be recorded as de-identified data in an excel document.

10.4. Data analysis

All data will be analyzed in accordance with the statistical analysis plan (SAP) to be developed at the beginning of this study. Both primary and secondary analyses will be based on an intention-to-treat (ITT).

The study's primary objective is to estimate the relative improvement in medication adherence among children using the BreatheSmart compared to control participants using "standard of care".

Important secondary objectives include the extent to which the Cohero system improves:

- asthma control as measured by ACT

- FEV1, FEV1/FVC ratio, FEF25-75 and FeNO compared to standard of care, and the correlation between changes in medication adherence from baseline and changes in FEV1 and FEV1/FVC ratio.
- the overall number of provider visits for asthma-related adverse outcomes (number of exacerbations leading to Provider intervention, ER visits, hospitalizations, or requiring oral systemic corticosteroid therapy)
 - Missed school days

Data results may be used to inform a study of a larger cohort with similar focus with regard to sample size estimates, efficacy of the BreatheSmart platform, feasibility in a low-income pediatric population and study design.

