Telemanagement of chronic diseases is increasingly being employed to improve medication adherence and health outcomes, and has been shown to be cost-effective.¹³ A recently developed process model for optimal asthma care demonstrates the need for improved understanding of patient medication use behavior and how adherence interventions can impact clinical outcomes.¹⁴ A number of studies have improved medication adherence through incorporation of electronic reminders such as text messages across the spectrum of chronic diseases.¹⁵ Recently a number of studies have looked specifically at the use of such messages along with medication-use tracking in asthma have been able to show mean improvement in adherence from 10-52 percentage points.¹⁶⁻²³ While promising, these interventions have focused on the use of audiovisual reminder systems^{16, 21-23} that rely on having access to the inhaler itself or are simply based on SMS messages.^{17,18} Such interventions are limited in their ability to engage participants for improved disease self-management and self-monitoring compared to more comprehensive approaches, known to be key for sustained asthma telemanagement and mHealth approaches.¹³

Importantly, mobile applications allow for better sustained patient engagement and have been successfully implemented in other disease spaces to improve medication adherence and outcomes.¹³ Mobile applications offer the opportunity to be scaled to the U.S. population-at-large and can be sustained due to the front-end cost of development and low staff resources required for maintenance once the product is built. Additionally, the ability to relay adherence data directly to clinicians either via a patient portal or into the EMR provides opportunity to direct care coordination efforts and resources towards those participants who are most in need, and provides information that can be used for point-of-care treatment decision making.

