6. STUDY DESIGN

This is a prospective, randomized, controlled study of children with persistent asthma who are managed on daily inhaled corticosteroids (ICS). 75 children will be randomized **2:1** into one of two arms:

- 50 children will be randomized to BreatheSmart, comprised of:
 - BreatheSmart mobile application that tracks medication usage and sends real time reminders
 - HeroTracker sensor that counts dosage and monitors real-time medication adherence
 - CoheroConnect provider portal that allows the Investigator to monitor real-time adherence and to provide targeted outreach to children with low adherence (intervention arm)
- 25 children will be randomized to “standard of care” (control arm). These patients are reminded to adhere to the prescribed standard of care therapy provided by their clinician during their clinical encounters and when the family calls to report an illness.

6.1.Endpoints

6.1.1 Primary:

The study's primary objective is to estimate the relative improvement in medication adherence among children using BreatheSmart with feedback compared to control at 6 months.

6.1.2 Secondary:

Important secondary objectives include the extent to which BreatheSmart system improves the following when compared to control from baseline to 6-months:

- asthma control as measured by the Childhood Asthma Control Test (ACT)
- lung function as measured by FEV1 and FEV1/FVC ratio compared to standard of care
- the correlation between changes in medication adherence and changes in FEV1 and FEV1/FVC ratio.
- the overall number of provider visits for asthma related adverse events (number of exacerbations leading to acute Provider intervention, ER visits, hospitalizations, or requiring oral systemic corticosteroid therapy)
- number of missed school days

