8.4. Follow-up

All participants in both groups will be seen at 90 and 180 days' post randomization (+/-20 days) correlating with routine pulmonary clinic follow up and East and West Primary Care Follow up where the following assessments will be recorded:

- Medication changes/refills (obtained through pharmacy record)

- FEV1, FEV1/FVC, FEF25-75 and FeNO per clinical standard of care (only assessed in the Pulmonary clinic)
- Child Asthma control test (ACT) questionnaire
- Serious Adverse Events will be recorded at each visit
- Missed school days
- PedsQL asthma module (patient and parent report)
- Test of Adherence to Inhalers
- Exacerbation of asthma episodes (obtained through self-report and chart review) requiring:
 - Doctor visits outside of standard of care
 - ER visits
 - Hospitalizations

In addition, active participants (test group) will be continuously monitored via the CoheroConnect dashboard which allows the Investigator to monitor the child's medication adherence in real time. If a period of participant inactivity of 3 days is registered in the system, the Investigator (or designee) will be notified and he/she will be prompted to contact the participant to remind them to take their medication as prescribed. The Investigator or designee will review patient specific data (% adherence since last visit and graph of adherence patterns over time since enrollment) through the CoheroConnect dashboard within two days before a follow up visit. At the follow-up visit, these data will be reviewed with the patient and parent/caregiver. The adherence rate and barriers identified will be discussed and, if necessary, personalized strategies for improvement will be devised. These data will also be shared with the clinician during these follow up visits. Medication adherence data for control participants will be obtained by measure of pharmacy record refill information and self-report (Test of Adherence to Inhalers) throughout the duration of the study.

We understand that the self-report of missed school days due to asthma may be unreliable and subject to recall bias, however, this is the method we currently use clinically to assess this measure.

If a participant is unable to complete the follow-up visit at their routine pulmonary appointment, the coordinator will either mail, text a link, or email a link of the follow-up surveys to the participants. They will be reminded 3 times via text, email or phone to complete the follow-up questionnaires.

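### The secondary exacerbation outcome is defined differently in sections 6.1.2, 8.4, 9.1 and 10.4, and the broadest reading lets discretionary medication changes enter the count at different rates by arm

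*Combined protocol and SAP*

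**What the plan says.** Section 6.1.2 sets the secondary endpoint as the "number of exacerbations leading to acute Provider intervention, ER visits, hospitalizations, or requiring oral systemic corticosteroid therapy". Section 10.4 gives the analysis version as the "number of exacerbations leading to Provider intervention, ER visits, hospitalizations, or requiring oral systemic corticosteroid therapy", without the word *acute*. Neither section says what counts as a provider intervention.

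Section 9.1 sits under adverse-event reporting. It opens with "An exacerbation of asthma requiring an intervention by the investigator must be recorded", and the first of its four alternatives is "change in/or addition of prescribed medications for the treatment of asthma, or". That alternative stands beside extra doctor visits, ER visits and hospitalization, and does not depend on any of them.

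Section 8.4 lists what is collected on exacerbations at 90 and 180 days: doctor visits beyond usual care, ER visits and hospitalizations. Oral steroid courses appear in the baseline lists (8.3.1, 8.3.2) but not in this one. Medication changes and refills are a separate item, taken from pharmacy records.

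For active-arm children, 8.4 adds real-time monitoring. After 3 days of inactivity the investigator or designee is notified, and "he/she will be prompted to contact the participant to remind them to take their medication as prescribed". Dashboard data are reviewed with the family at follow-up, and "These data will also be shared with the clinician during these follow up visits". Section 6 lists the outreach as part of the intervention: "to provide targeted outreach to children with low adherence (intervention arm)". The Introduction says that relaying adherence data to clinicians "provides information that can be used for point-of-care treatment decision making". Section 8.2 states that the trial is open.

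**The concern.** The objective is whether BreatheSmart lowers the number of provider visits for asthma-related events. To answer it, the count must mean the same thing in every section and respond to asthma in the same way in both arms.

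The four descriptions do not give the same count. The broadest reading takes the unqualified provider intervention of 10.4 and fills it in from 9.1. A medication change made for an exacerbation at a scheduled visit then counts. That is a prescriber's decision, and only for active-arm children is the prescriber described as holding dashboard adherence data. The data could push the count either way. They may prompt a change that would not otherwise be made, or they may lead the clinician to work on adherence and leave the prescription alone. A difference between arms could then reflect recognition or prescribing instead of exacerbations. Section 10.4 says that the results may inform the sample size and efficacy expectations of a larger study, so an estimate of unclear meaning could be carried forward.

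**Working it through.** **Step 1. The definitions side by side.**

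| Section | Must provider contact be acute or unscheduled? | Does a medication change suffice? | ER visit, hospitalization | Oral steroid course |
|---|---|---|---|---|
| 6.1.2 endpoint | Yes (acute) | Not listed | Yes | Yes |
| 8.4 follow-up list | Yes (beyond usual care) | No; recorded as a separate item | Yes | Not listed |
| 9.1 safety reporting | Only for the doctor-visit item | Yes, given an exacerbation that needs investigator intervention | Yes | Not named; could fall under added medication |
| 10.4 analysis | No qualifier | Neither listed nor excluded | Yes | Yes |

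**Step 2. Two cases that the definitions classify differently.**

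- *An exacerbation is recognised at the scheduled 90-day visit, asthma medication is changed, and there is no other contact.* 6.1.2: no, unless a routine visit is called acute. 8.4: no. 9.1: yes. 10.4: yes if provider intervention is read through 9.1, otherwise unclear.
- *An exacerbation is treated with an oral steroid course, with no extra doctor visit, ER visit or admission.* 6.1.2 and 10.4: yes. 9.1: yes, as an added medication. 8.4 exacerbation list: no item for it.

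**Step 3. Where the arms differ.** Clinician access to dashboard data and contact after 3 inactive days are described for active-arm children only. For controls, 8.4 gives refill records and the Test of Adherence to Inhalers, and says nothing about passing these to the clinician. The first case in Step 2 depends on a clinician's decision and is the most exposed. Extra doctor visits and oral steroid courses also involve some discretion. ER visits and hospitalizations are less exposed.

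**Step 4. Size, for illustration only.** The plan has no figure to reproduce: section 7.2 gives no sample-size calculation, and no event rate appears anywhere. The allocation is consistent: 75 × 2/3 = 50 and 75 × 1/3 = 25.

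Assume 0.5 countable events per child over 6 months in both arms: 50 × 0.5 = 25 active, 25 × 0.5 = 12.5 control. Let p be the number of events per active child added or removed only by recognition or prescribing.

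Spurious rate ratio = (0.5 ± p)/0.5

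| p | Events added: active events, ratio | Events removed: active events, ratio |
|---|---|---|
| 0.05 | 27.5, 1.1 | 22.5, 0.9 |
| 0.10 | 30, 1.2 | 20, 0.8 |
| 0.20 | 35, 1.4 | 15, 0.6 |

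For precision, take 30 against 12.5 events. The standard error of the log ratio is √(1/30 + 1/12.5) = 0.337. The approximate 95% interval is 1.2 × exp(±1.96 × 0.337), or 0.62 to 2.32. A distortion of this size is well inside sampling error.

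**Step 5. How often it would produce a significant result.** This is a Poisson simulation with 20,000 runs, 50 against 25 children, and a two-sided 0.05 t-test on counts. The t-test is an assumption, because 10.5 names no method for this outcome. The true exacerbation rate is equal in both arms, and 50% of control exacerbations are recorded as provider intervention. The columns are true exacerbations per child over 6 months.

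| Share recorded, active arm | 0.5 | 1 | 2 |
|---|---|---|---|
| 50% (no difference) | 4.9% | 5.0% | 4.8% |
| 60% | 5.7% | 7.4% | 11.1% |
| 40% | 8.0% | 10.3% | 14.7% |
| 75% | 12.0% | 22.3% | 41.6% |
| 25% | 24.9% | 41.4% | 68.1% |

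Small recording gaps do little, and large ones matter. The documents do not show which applies.

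**The case against.** The best defence is that 9.1 is a safety-reporting section, and nothing says that it defines the secondary outcome. It also requires an exacerbation, so a dashboard-prompted adjustment without one does not qualify. The outcome's lead-in in 6.1.2 and 10.4 speaks of provider visits, which does not naturally describe a routine visit with a prescription change. The 8.4 list already limits doctor visits to those beyond usual care and keeps medication changes apart. All of this stands, and the narrower reading may well be the intended one. But the protocol never says which section governs, and 8.4 cannot serve as the definition while it omits oral steroid courses. Pharmacy records under 8.4 might recover those courses, but the section does not tie them to exacerbations.

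The second defence is that the portal and the outreach are components of the intervention, so changes in provider visits that arise through them belong to its effect under intention-to-treat. This stands for fewer exacerbations through better adherence. It does not cover differences in what gets labelled an event.

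A reader might infer that outreach calls themselves inflate the active-arm count. The documents do not support this. The call is a medication reminder, not a symptom enquiry, and exacerbations are obtained by self-report and chart review in both arms on the same visit schedule. Detection through calls is possible but conjectural. A reader might also infer that clinicians of control children are barred from adherence data. That rests on silence. Children are randomized individually within shared clinics, so the contrast lies between children and not between two sets of clinicians.

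**Conclusion.** The inconsistency is established by the text: *acute* is in 6.1.2 and not in 10.4, a medication change alone is enough in 9.1, and oral steroid courses are missing from 8.4. It is also established that the trial is open and that sharing data with the clinician and outreach are described only for active-arm children. On the reading that joins 10.4 to 9.1, discretionary medication changes at scheduled visits can therefore enter the count at different rates by arm, in either direction.

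The stronger conclusion, that the intervention by itself drives this outcome or makes the comparison invalid, does not follow. It needs 9.1 to be the governing definition, which the protocol does not say. It also ignores that ER visits and hospitalizations are less exposed and that part of any reduction would be a genuine effect.

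The size of any bias is unknown. The ratios of 1.1 to 1.4 and 0.9 to 0.6, and the simulated rejection rates, rest wholly on assumed rates. The point concerns one secondary outcome of an exploratory trial and leaves the primary adherence analysis untouched. It is still worth correcting, because the correction is cheap and changes what is counted.

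**What to change.** 1. Use one definition in 6.1.2, 8.4 and 10.4: exacerbations with an acute or unscheduled provider visit beyond usual care, an ER visit, a hospitalization or an oral systemic corticosteroid course. Add the oral steroid item to the 8.4 list.
2. Collect it in the same way in both arms at 90 and 180 days.
3. State that 9.1 serves safety reporting and does not define this outcome.
4. Do not count medication changes made at scheduled visits. Tabulate them by arm.
5. Report each component separately, so that ER visits and hospitalizations can be read on their own.
6. Events that follow an outreach contact may be flagged and described, since 10.2 already requires communications with participants to be documented. Do not remove them from the comparison: controls have no outreach, so removal would delete events from the active arm only and favour the intervention.

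The cost is wording in four sections, one added item on the follow-up form, an optional flag and one extra table. The small downside is fewer countable events. Nothing in the children's care changes.
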